The effects of EA do dissipate, but these techniques do not necessarily need to be started before the incision or insult. Syuu et al. looked at the effects of EA at PC 6 in a hemorrhaging dog model. EA was started 30 after the hemorrhage was initiated. This study illustrated that stimulation of PC 6 prevented the fall in left ventricular performance and rise of plasma vasopressin. Improved left ventricular performance was also noted as long as EA was maintained. Once the stimulation was stopped, the effects dissipated over 120 minutes. This confirmed that stimulation of the point can be initiated after incision or insult, and that the effects of EA dissipate over time.⁹

Though stimulation at PC-6 has been done by many investigators, other points have been used as well for cardiovascular surgery. Zhou et al. studied 100 patients with standard general anesthesia and 100 patients with combined acupuncture plus midazolam.¹⁰ Those in the acupuncture group had significantly less opiate use, fewer pulmonary infections, shorter ICU stays, and lower cost. The points stimulated for this study were ZhongFU (Lung 1), Lung 7 and PC 4.¹⁰ Points used by Chi et al. included Lung 1, Chize (Lung 5) and PC 4.¹⁰ Their acupuncture group needed significantly less blood transfusion, less antibiotics for pulmonary infections, and had shorter duration of hospitalization, shorter ICU stays and lower medical costs. They stimulated their points at 3-4 Hz and 2.0-2.2 mA for 20 minutes.¹¹ A common point in these papers was stimulation at PC 4 and PC 6. Another advantage of these points is that they are distal to the surgical field and usually readily accessible.

Stimulation at PC 6 has advantages in the kidney as well. Fifty percent of children undergoing cardiovascular surgery develop at least stage 1 acute kidney injury (AKI). It is speculated that this AKI is related to activation of sympathoexcitatory inputs modulated through renal afferent nerves. Recent studies have tried to decrease this incidence by modulation of the renotubular feedback loop with adenosine receptor antagonism¹¹ This has been able to decrease the need for renal replacement therapy after CPB, but has not been shown to prevent the development of AKI.¹² EA can affect sympathoexcitatory inputs. Yu et al. stimulated rabbits in an AKI model and found stimulation at PC 6 and ST 36 using a dense disperse wave at 2 and 15 Hz with 1 mA reduced morphologic renal damage and attenuated renal tubular apoptosis.¹³

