Predicated on the primary aim, the sample size for this pilot study we used a two-sided two-sample t-test with unequal variance t-test with an alpha level of 0.05 and power of 80%. A morphine equivalent dose of 0.71 mg/kg was used for the control group and 0.57 mg/kg for the acupuncture group. This represents a conservative 20% change between the control and acupuncture group. The standard deviation of the control group was estimated to be 0.3 mg/kg for the control group and 0.2 for the experimental group. **The total estimated sample size is 108 patients, over the two years, with 54 allocated to each group.** Historically, we would have had a potential enrollment and retention of approximately 74 patients per year accounting for a 25% non-consent rate and a 2% drop-out rate. This project is well powered for statistical significance and feasibility for a 2-year study.

Data collection:

The data will be retrieved from the EMR and imported or entered into a secured EXCEL database.

Statistical analysis plan:

For all aims, univariate statistics (e.g. mean, median, standard deviation, min, max and skew) will be used to describe the collected data. Parametric approaches (e.g. t-test, Pearson's correlation, and chi-squared test) will be used when the data satisfy the required statistical assumptions; they will be used to compare the demographic and clinical characteristics between treatment and control. If the distributional assumptions are untenable, then the Mann-Whitney test, Spearman

correlation, and Fisher's exact test will be used. We will use the Box-Cox or the exponential transformation when the absolute value of skew is greater than 0.4.

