To address the overall difference between the control and the acupuncture group, we will look at the score changes between baseline and 48 hours. For the continuous outcomes, a t-test based on the difference in outcome will be used to compare the two treatment groups. For the categorical outcomes, a logistic regression model (generalized linear model with binary or multinomial outcome) will be used to compare the two treatment groups' at baseline and 48 hours. The generalized linear hypothesis methodology will be used to contrast the two time points. This approach will provide consistency of modeling methodology for the secondary analyses. Adjusted models will be considered (e.g. glm regression with identity and/or logit links) to account for any data imbalances, potential confounders, etc. Minimally, a RACHS score adjustment will be assessed for its relevance.

A secondary analysis will be used to describe the longitudinal (repeated measures) outcome trends. A generalized linear mixed-effects regression model will be used for longitudinal data. Both unadjusted and adjusted trends will be assessed. We will account for both heteroscedasticity and autocorrelation variance-covariance structures. The generalized linear model approach will permit trend characterizations for either continuous or categorical outcomes under the same generalized linear model framework.

[figure not shown]
All results, predicated on formal hypothesis testing methodology, will use an alpha-level of 0.05 for statistical significance. Bonferroni or Scheffe adjustments will be used, when appropriate, to retain the family-wise alpha level of 0.05 when performing multiple tests under the same global hypothesis or construct. Every effort will be used to ensure all relevant information is collected. In the event of missing data, generalized estimating equations for longitudinal analysis will be used. All statistical analysis will be done using the most recent version of the R language for statistical computing and graphics.

Tentative time table: Approximately 2 years to enroll 108 subjects.

[figure not shown]
References:

- 1) Instruction manual for KWD-808I Multipurpose health device, Ying Di page 21.
http://www.ib3health.com/products/Acupunctoscope/KWD808_I.asp#808I_Instruct [Accessed Sept. 5, 2016]

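### The SAP names no order-respecting model for AKIN stage or inotropic group; an unordered multinomial test could cost roughly 11 to 20 points of power under assumed odds ratios of 0.4 to 0.5

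*Combined protocol and SAP*

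**What the plan says.** The outcome paragraph of the Statistical analysis plan sends continuous outcomes to a t-test on the change from baseline to 48 hours. Where an outcome is categorical, the text reads: "a logistic regression model (generalized linear model with binary or multinomial outcome) will be used to compare the two treatment" arms. The time points for that comparison are baseline and 48 hours. A generalized linear mixed model follows for longitudinal trends, continuous or categorical. Every formal test "will use an alpha-level of 0.05 for statistical significance".

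Appendix B lists AKIN score as stages 1 to 3, recorded every 6 hours, and inotropic score as groups 1 to 5. The inotropic appendix assigns the group from the highest support level in either the first or second 24 hours, so each child has one group. Pneumonia is a yes/no indicator. The renal secondary objective is worded as AKI incidence. No ordinal, cumulative-logit or proportional-odds model appears anywhere. A Mann-Whitney fallback is named, but alongside the comparison of demographic and clinical characteristics.

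The only category frequency given is in the Background: "Fifty percent of children undergoing cardiovascular surgery develop at least stage 1 acute kidney injury (AKI"). The split over stages 1 to 3, the inotropic group distribution and a target odds ratio are not given.

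**The concern.** AKIN stage and inotropic group are severity scales, and the natural question is whether electrostimulation shifts children towards the milder end. An unordered multinomial model asks instead whether the two distributions differ in any way. It produces three or four odds ratios per outcome, which can point in different directions, and an overall test that can be significant without showing benefit or harm. The worst categories will be sparse with 54 children per arm.

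At stake are the renal secondary objective and the comparison of myocardial support. A real shift in severity would be harder to detect than the same data allow. Adjustment adds to the burden. The plan says RACHS adjustment will at least be assessed, and RACHS has six categories. If all six occur, an unordered model needs 3 × (1 + 1 + 5) = 21 parameters for AKIN and 4 × 7 = 28 for inotropic group. A cumulative-logit model needs 3 + 1 + 5 = 9 and 4 + 1 + 5 = 10.

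**Working it through.** **1. The plan's own figure.** The Sample size section uses a "two-sided two-sample t-test with unequal variance t-test with an alpha level of 0.05 and power of 80"%. For the effect to be detected, it states: "A morphine equivalent dose of 0.71 mg/kg was used for the control group and 0.57 mg/kg for the acupuncture group". The standard deviations are given as "estimated to be 0.3 mg/kg for the control group and 0.2 for the experimental group". At 54 per arm the standard error is √(0.3²/54 + 0.2²/54) = 0.0491 and the noncentrality is 0.14/0.0491 = 2.85. Power by the noncentral t is 80.6% (79.9% at 53 per arm), so 54 per arm reproduces. This concerns opiate dose; no power is stated for any categorical outcome.

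**2. Inputs for the check.** From the documents: "The total estimated sample size is 108 patients, over the two years, with 54 allocated to each group"; alpha 0.05 two-sided; 50% any AKI. Assumed: the remaining category splits, proportional odds, and a common odds ratio (OR; electrostimulation against sham, for being in a worse category) of 0.4 or 0.5. AKIN with no AKI as stage 0 has 4 categories, so 3 df if unordered. Inotropic group has 5, so 4 df.

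**3. One case by hand.** Take sham AKIN at 50/30/12/8% and OR 0.4. The tail probabilities 0.50, 0.20 and 0.08 have odds 1, 0.25 and 0.087. Multiplying by 0.4 gives 0.40, 0.10 and 0.035, which convert back to 0.286, 0.091 and 0.034. The treated split is 71.4/19.5/5.7/3.4%.
- Ordinal (Whitehead formula): z = |ln OR| × √[N(1 − Σp̄³)/12], where p̄ is the mean of the two splits. With Σp̄³ = 0.240, z = 0.916 × √(108 × 0.760/12) = 2.40. Power is Φ(2.40 − 1.96), about 67%.
- Unordered: the same noncentrality, 2.40² = 5.75, spread over 3 df with critical value 7.81, gives about 50%.

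**4. Simulation.** 20,000 trials per setting, comparing the multinomial likelihood-ratio test with the proportional-odds score test (tie-corrected rank-sum).

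| Outcome, assumed sham split (%) | OR | Unordered | Ordinal | Difference |
|---|---|---|---|---|
| AKIN 50/30/12/8 | 0.4 | 52% | 66% | 14 |
| AKIN 50/30/12/8 | 0.5 | 33% | 45% | 12 |
| Inotropic 35/25/20/10/10 | 0.4 | 53% | 72% | 19 |
| Inotropic 35/25/20/10/10 | 0.5 | 33% | 50% | 17 |

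AKIN splits of 50/25/15/10 and 50/35/10/5 follow the same pattern, and across splits and repeat runs the AKIN difference is about 11 to 15 points. Three other inotropic splits (equal, 40/25/15/10/10, 30/30/20/12/8) give 16 to 20. A more skewed one (60/20/10/6/4) gives 11 to 15. Under the null the unordered test rejects in 5.6 to 6.9% of trials and the ordinal test in about 5%, so the unordered power is slightly flattered.

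**5. Where the size changes.**
- Weaker effect (OR 1/1.5): 3 to 8 points in the main settings.
- AKIN at 48 hours with 80% at stage 0 (assumed 80/13/5/2): 20% against 25% at OR 0.5, and 29% against 37% at OR 0.4, so 4 to 8 points.
- Binary any-AKI instead of multinomial, split 50/30/12/8: binary 63% against ordinal 65% at OR 0.4, and 41% against 45% at OR 0.5; the gain is 2 to 3 points before rounding.
- Any AKI falling from 50% to 30% with an unchanged severity mix: unordered 43%, ordinal 55%, binary 57%.
- Treatment only moves stages 2 and 3 into stage 1 (50/25/15/10 against 50/42/5/3): unordered 65%, ordinal 14%.

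**The case against.** The strongest reply is that the plan does not commit itself to ignoring order. It says binary or multinomial, assigns no outcome to either, and does not state the link; a cumulative-logit model also has a multinomial response. AKI incidence fits the binary model, against which the ordinal gain is 2 to 3 points or slightly negative. The underlying inotropic score is numeric and could go to the t-test. The planned comparison is at 48 hours, whereas the 50% figure is the proportion who ever develop AKI. The ordinal model also does badly if proportional odds fails as in the last case above.

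Most of this limits the size of the point rather than removing it. If multinomial refers to neither AKIN stage nor inotropic group, it applies to no outcome in Appendix B, so the assignment is a strong inference, though not stated text. If a cumulative link was intended, one sentence would say so. The warning about proportional odds stands in full, and the remedy has to carry it.

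A reader might infer that 11 to 20 points is a loss built into this plan. The documents do not support that: they supply no odds ratio, no stage split and no group distribution. A reader might also infer that the longitudinal multinomial model cannot be estimated in 108 children. That may be a reasonable worry, but no calculation here shows it.

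**Conclusion.** The point holds as a cheap improvement to the analysis of secondary outcomes. The plan names no order-respecting model for its two ordered multi-category outcomes. Read as unordered, the named model spends 3 or 4 df, gives no single direction and runs at about 6% under the null. Its power cost at 54 per arm is about 11 to 15 points for AKIN stage and 16 to 20 for inotropic group. Those figures are conditional on proportional odds, an odds ratio of 0.4 to 0.5, the assumed splits and an unordered likelihood-ratio test. They are smaller for weaker effects, for a heavily skewed inotropic distribution, or with few children above stage 0 at 48 hours.

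It would be wrong to conclude that an ordinal model is always better, that AKI incidence is badly served by the binary model, or that the trial's sample size is affected. The first fails when the effect is confined to the severe stages, the second is contradicted by the 2 to 3 point gap, and the third does not follow because 108 was set on opiate dose.

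**What to change.** In the outcome paragraph of the Statistical analysis plan, name the model and time point for each categorical outcome before unblinding:
- **Worst AKIN stage over 48 hours** (0 = no AKI): cumulative-logit model, one common odds ratio with confidence interval.
- **Inotropic group**: the same model, on the single worst value per child. As defined, it has no baseline and no repeated values, so remove it from the baseline-to-48-hour contrast and from the mixed model.
- **For both**: a stated check of proportional odds, and the table of stages or groups by arm beside the odds ratio.
- **AKI incidence and pneumonia**: keep binary logistic regression.
- **6-hourly AKIN stage**: cumulative-logit mixed model. This is the only ordered outcome here for which a mixed model applies.

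The cost is SAP wording; standard R packages fit these models, and no data collection or sample size changes. The downside is that the common odds ratio is an average over cut-points and the model can miss an effect confined to the severe stages, which is why the check and the table belong in the plan.

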The primary objective of this study is to identify whether electroacustimulation is a beneficial anesthesia adjunct in children undergoing procedures on their congenital heart defects. Does it decrease myocardial injury and or need for myocardial support. Differences between the groups Troponin I levels pre-operative and six hours postoperative will be evaluated.

Secondary Objectives:

1) Evaluate the incidence discomfort in the post- operative period.

To evaluate the incidence and severity of pain assessed by using age appropriate West Virginia University Hospital approved nurse guided pain scoring the Neonatal/Infant Pain Scale (NIPS) (children age birth to 2 months) FLACC (2 months to 7 years or unable to communicate, or VAS(age 8-18) every 2 hours for 48 hours post procedure.

2) Determine the incidence of Acute kidney injury (AKI) between these two treatment groups. Acute Kidney Injury will be evaluated by AKIN criteria. Creatinine and urines will be measured at 6, 12, 24 and 48 hours after bypass.

Need for post-operative myocardial support:

To assess the need for myocardial support an inotropic score will be used and compared between the two groups. The Inotropic score will be evaluated every 6 hours for 48 hour between the 2 groups

Study Design:

This is a single site, randomized, blinded, sham controlled, parallel group study to identify whether electroacustimulation is a beneficial anesthesia adjunct in children undergoing procedures on their congenital heart defects.

Study subjects age's birth to eighteen years, undergoing cardiac surgery for their congenital heart lesions will be considered for entrance into the study. The randomized subjects will receive either electrostimulation or sham during their surgery for CHD. Subjects are expected to remain in the hospital 48 hours post procedure. Standard of care blood samples will be obtained pre-operative and post-operative. The only study specific blood sample will be Troponin I levels which will be obtained presurgically after the lines have been placed and a 6 hours post bypass/aortic clamp removal. Urine samples will be obtained pre-surgically after placement of the Foley and every 6 hours post bypass for 48 hours while the Foley catheter is still in place .

Number of Subjects planned:

Approximately 108 patients, over the two years, with randomization of 54 allocated to each group.

- Electroacustimulation (treatment) frequency will be at 2Hz and 100 Hz the amplitude will be 1000mA.

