Group 2: Receive sham electroacustimulation (control) will not have stimulation. Subjects will undergo procedures on their congenital heart defects.

Blind:

The anesthesia provider will be blinded as to whether the electroacustimulation device is actually turned on or not. The research coordinator will hold the blind. The electroacustimulation machine will be placed in an opaque bag to secure the blind. The current is below the threshold to stimulate the muscle so that no movement will be visible. It is also below the sensory threshold so that it will not produce any discomfort in the subjects.

Stimulation/Sham will be continued until the patient is ready for transport to the PICU.

Post-Operative: PICU

Stimulation/Sham will be discontinued.

PICU care givers will be blinded as to which group the patients were randomized.

Subject comfort will be assessed using age appropriate West Virginia University Hospital approved nurse guide pain scoring based on Universal Pain Assessment Tool or the Neonatal/Infant Pain Scale (NIPS) will be recorded in the electronic medical record (EMR) every 6 hours for 48 hours.

The amount of opiate infused, Nausea, Vomiting, and urine output will be assessed every 6 hours for the first 48 hours and recorded in the EMR.

Research blood samples for troponin I will be obtained at 6 hours post surgery. Total amount of 7cc of blood will be

obtained for this study. WVUH lab will process samples.

Research urine samples (.05-2cc) will be collected at 6, 12, 24, and 48 hours after bypass. The urine samples will be stored in a -80 degree freezer and analyzed by ELISA testing at the end of the study for Superoxide dismutase, Neutrophil gelatinase – associated lipocalin (NGAL), WNT4.

AKIN criteria will be used to evaluate AKI every 6 hours. Inotropic score will be recorded every 6 hours.

Daily chest x-ray will be used to assess pulmonary status.

The AKIN criteria, inotropic scores, chest x-ray and creatinine levels, (used for AKIN), are standard of care measurements and the data will be collected for this research project.

An Electrostimulation Documentation Guide has been developed for the staffing. (Appendix A2)

Tool/Instruments to be used in data collection:

Tools and instruments for data collection: secured Excel data base; Neonatal/Infant Pain Scale (NIPS); AKIN stage; Inotropic Scores; RACHS categories (Appendix A3-6).

Variables:

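### The AKI objective is incidence over 48 hours, but the planned tests use status at baseline and 48 hours or describe trends, so neither estimates it

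*Combined protocol and SAP*

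**What the plan says.** Under Secondary Objectives, item 2 is: "Determine the incidence of Acute kidney injury (AKI) between these two treatment groups". AKI is to be judged by AKIN criteria, and the same item adds: "Creatinine and urines will be measured at 6, 12, 24 and 48 hours after bypass". The Post-Operative: PICU section states: "AKIN criteria will be used to evaluate AKI every 6 hours". The documentation guide has eight AKIN rows, from 6 to 48 hours after bypass, and Appendix B repeats the 6-hourly schedule with the scale given as stages 1 to 3.

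The Statistical analysis plan gives one rule for all outcomes: "we will look at the score changes between baseline and 48 hours". For categorical outcomes this becomes a logistic or multinomial model comparing the arms at those two times, after which "The generalized linear hypothesis methodology will be used to contrast the two time points". Then: "A secondary analysis will be used to describe the longitudinal (repeated measures) outcome trends", using a generalized linear mixed model. An adjustment for RACHS score is to be considered.

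No section derives a per-child variable such as any AKIN stage, or worst AKIN stage, within 48 hours.

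**The concern.** Incidence over 48 hours counts every child who meets AKIN at any time in that window. Status at 48 hours counts only those who still meet it at the end. The two agree only if no AKI resolves before 48 hours.

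Two errors become possible. If treatment prevents AKI that would have resolved anyway, the main comparison does not show it. If treatment leaves incidence unchanged but speeds recovery, a lower 48-hour prevalence could be reported under an objective worded as incidence. The mixed model may reveal the early pattern, but it gives time-specific odds, not the proportion of children ever affected. Objective 2 is therefore left without an estimate of its own quantity.

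**Working it through.** **1. The plan's own figure.** The only stated sample size rests on opioid dose: 0.71 versus 0.57 mg/kg, SDs 0.3 and 0.2, two-sided alpha 0.05, power 80%. A Welch t-test with these inputs has power 79.9% at 53 per arm and 80.6% at 54, so 54 per arm (108 in total) reproduces. The documents give no power for AKI.

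**2. What the baseline term can contribute.** The baseline part of the documentation guide has rows for creatinine and urine but none for AKIN, and the score form starts at 6 hours. The AKIN creatinine criterion in Appendix 4 is a rise from a reference value, so no baseline stage is expected. Suppose baseline is 0/54 in each arm (assumption) and 48-hour status is 27/54 versus 14/54. A logistic fit that ignores within-child correlation gives a baseline-to-48-hour log odds of about 24.6 with a standard error of about 17,800, which is not estimable. The between-arm log odds ratio at 48 hours is ln[(14/40)/(27/27)] = −1.05 and is estimable. What remains is thus a comparison of prevalence at 48 hours.

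**3. Inputs for the size.**
- Control incidence I = 0.50 for at least stage 1 (Background).
- n = 54 per arm (Sample size).
- Assumed, not in the documents: relative reductions of 50%, 40% and 20%, and the share r of AKI cases that still meet AKIN at 48 hours. The 20% matches the size of the opioid planning change ("This represents a conservative 20% change between the control and acupuncture group").

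Prevalence at 48 hours = I × r. Control-arm cases not counted = 54 × 0.50 × (1 − r) = 27 × (1 − r): 6.75, 13.5 and 20.25 children for r = 0.75, 0.50 and 0.25.

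**4. Power.** The test is the uncorrected two-sided chi-square at alpha 0.05: χ² = ((x₁ − x₂)/n)² / [2p̄(1 − p̄)/n], rejecting above 3.84. Rejection probabilities are summed exactly over both binomial distributions.

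| Resolved by 48 h (both arms) | Control prevalence at 48 h | Power, 50% reduction | 40% | 20% |
|---|---|---|---|---|
| 0% (same as any AKI) | 50% | 77.9% | 56.6% | 16.9% |
| 25% | 37.5% | 58.6% | 39.8% | 13.3% |
| 50% | 25% | 38.9% | 25.6% | 9.5% |
| 75% | 12.5% | 19.5% | 13.6% | 6.8% |

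**5. Direction.**
- Treatment prevents only cases that would resolve: any AKI is 50% versus 25% and 48-hour status is 25% versus 25%. The test rejects in 77.9% of trials on any AKI and in 4.9% on 48-hour status.
- Incidence 50% versus 30% with persistence 30% versus 50%: 0.50 × 0.30 = 0.15 and 0.30 × 0.50 = 0.15. A real difference in incidence vanishes at 48 hours.
- Incidence 50% in both arms with unequal persistence:

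| Persistence to 48 h | Prevalence at 48 h | 48-hour test rejects |
|---|---|---|
| 75% vs 25% | 37.5% vs 12.5% | 87.0% |
| 70% vs 30% | 35% vs 15% | 68.2% |
| 60% vs 40% | 30% vs 20% | 22.2% |

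In all three rows the test on any AKI (50% versus 50%) rejects in 4.4% of trials.

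**The case against.** The analysis text is a template for every categorical outcome and never names AKI. The plan also promises descriptive statistics for all aims and lists chi-squared and Fisher tests, so a simple AKI proportion by arm might be intended. For the inotropic score, the appendix groups patients by the highest support level in either period, which suggests a forgotten definition rather than a deliberate choice of 48-hour status. The mixed model would make early divergence or later recovery visible. The non-estimable contrast costs little, since the between-arm comparison at 48 hours survives. The size rests on assumed resolution shares, and at a 20% reduction power is poor under either definition. Finally, a worst-stage endpoint depends on complete records: urine sampling is tied to the Foley catheter being in place, and one 6-hour output block cannot by itself establish a criterion of more than 6 hours.

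Much of this stands as a limit on size, and the remark about records is a real cost. It does not remove the mismatch. The chi-squared and Fisher tests are assigned to demographic and clinical characteristics, whereas AKIN is listed as an outcome, and no per-child AKI variable exists to enter them. The worst-value rule for the inotropic score has no counterpart for AKIN. Whatever was intended, the written rule for categorical outcomes is baseline and 48 hours.

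**Conclusion.** The concern holds. Followed as written, the plan compares AKI prevalence at 48 hours and describes trends; it does not estimate the share of children who develop AKI within 48 hours. This should be corrected, but it does not touch the primary objective, and the trial is a pilot not sized on AKI.

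The mismatch follows from the text alone. Its size does not: the loss runs from nothing, if no AKI resolves by 48 hours, to a fall from 78% to about 20% power, if three quarters resolve and treatment halves the risk. The scenarios with unequal persistence show that the error can also create an apparent benefit. All of these are illustrations. They take the Background's 50%, which is given without a time window, as incidence over 48 hours.

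**What to change.** In the Statistical analysis plan:

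- Define the AKI endpoint as the worst AKIN stage from end of bypass (or end of repair) to 48 hours, coded 0 to 3, one record per child.
- Compare stage 1 or higher between arms by logistic regression, with the RACHS adjustment already contemplated. A proportional-odds model of worst stage is optional.
- Drop the baseline-versus-48-hour contrast for AKIN and keep the mixed model as description.
- State how a child with missing creatinine or missing urine output is classified, and how 6-hour output blocks map to the AKIN duration criteria.
- In Appendix B, add code 0 for no AKI (a coding clarification).

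The cost is wording and one code, with no new sampling. Creatinine staging would rest on the 6, 12, 24 and 48 hour draws, and urine-output staging on the 6-hourly records. The small downside is that a worst-value endpoint is sensitive to gaps in those records, so the missing-data rule should be fixed before treatment codes are linked to the data.

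### The categorical analysis contrasts baseline with 48 hours, but the listed categorical outcomes have no scheduled baseline and the plan does not say how a child's two records are linked

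*Combined protocol and SAP*

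**What the plan says.** The Statistical analysis plan defines the overall group comparison as change from baseline to 48 hours. Continuous outcomes are compared by a t-test on each child's own difference, which respects the pairing.

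For categorical outcomes, a "logistic regression model (generalized linear model with binary or multinomial outcome) will be used to compare the two treatment" groups at the two times, and then "The generalized linear hypothesis methodology will be used to contrast the two time points". No child effect, clustering term, robust variance or baseline covariate is named for this step. The plan adds that the approach keeps the modelling consistent with the secondary analyses.

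Methods for correlated records appear in two other places. The secondary, longitudinal analysis says "A generalized linear mixed-effects regression model will be used for longitudinal data" and mentions autocorrelation structures. Generalized estimating equations (GEE) are named for longitudinal analysis if data are missing.

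The measurement times are in Appendix B. AKIN stage (1-3) and inotropic group (1-5) are listed 6-hourly to 48 hours, and pneumonia daily from the chest x-ray. None has a baseline entry. The baseline table of the documentation guide holds only creatinine, a urine sample, RACHS score and cyanosis. The AKIN table in Appendix 4 defines stage by a rise in creatinine or by low urine output over hours. The footnote to the inotropic classification assigns the group from the highest support level in either 24-hour period.

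**The concern.** A linear-hypothesis contrast of two time points needs both time coefficients from one fit, so the natural reading is that each child supplies two records to one model. That raises two questions.

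- **Does the baseline record exist?** If it does not, or if it is the same for everyone, the contrast has nothing to work on.
- **If there are two real records, how are they linked?** An ordinary generalized linear model treats records as independent, and two readings on one child usually are not.

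The incidence of AKI is a stated secondary objective, and the need for myocardial support is raised within the primary objective. An analyst who follows the rule literally could report no effect on AKI when the 48-hour data show one.

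**Working it through.** **1. The plan's own figure.** The Sample size section uses a two-sided "two-sample t-test with unequal variance t-test with an alpha level of 0.05 and power of 80"%, means of 0.71 and 0.57 mg/kg morphine equivalent, and standard deviations "estimated to be 0.3 mg/kg for the control group and 0.2 for the experimental group".
- Difference: 0.71 - 0.57 = 0.14. Mean variance: (0.3² + 0.2²)/2 = 0.065.
- Normal approximation: n per arm = 2 × 0.065 × (1.960 + 0.842)² / 0.14² = 52.06, so 53.
- Unequal-variance t-test with the noncentral t: power 0.799 at 53 per arm and 0.806 at 54. So 54 is the smallest number reaching 80%, and 108 in total is reproduced. This calculation uses a continuous outcome and does not depend on the present point.

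**2. No baseline variation.** Suppose every child is event-free before surgery and the 48-hour counts are 27/54 (control) and 16/54 (treated). The counts are illustrative.
- 48 hours alone: log odds ratio = ln(16/38) - ln(27/27) = -0.865. SE = √(1/27 + 1/27 + 1/16 + 1/38) = 0.404. z = -2.14, p = 0.032.
- Two-time model with arm, time and arm-by-time: the baseline log odds run to minus infinity. The fitted SE of the arm-by-time term is about 25,000 (an artefact of where the iterations stop) and p = 1.00.
- A likelihood-ratio test does not help. The model without the arm-by-time term already fits these counts perfectly (deviance zero to rounding), so the term adds nothing.
- The 48-hour difference is still in the data: in the model without that term, the arm coefficient is -0.865 with p = 0.032. It is the contrast of times that cannot show it.

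**3. Two real records per child.** The documents give no within-child correlation ρ and no event rates. Assumed: ρ from 0 to 0.7, event rates 0.3 and 0.5, 54 per arm.
- With equal variances at the two times, the true variance of a within-child contrast is (1 - ρ) times the independence variance. The SE is therefore too large by 1/√(1 - ρ), and the true type I error is 2[1 - Φ(1.96/√(1 - ρ))].
- Simulation of the arm-by-time contrast under no effect (40,000 runs per scenario):

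| ρ | SE ratio, formula | SE ratio, simulated | Type I error, formula | Type I error, simulated |
|---|---|---|---|---|
| 0.2 | 1.12 | 1.12 | 0.028 | 0.029 |
| 0.3 | 1.20 | 1.20 | 0.019 | 0.017-0.020 |
| 0.5 | 1.41 | 1.43 | 0.006 | 0.005-0.006 |
| 0.7 | 1.83 | 1.86-1.87 | <0.001 | <0.001 |

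- With the within-child covariance included, type I error is 0.051-0.055 throughout.
- Power, for 50% staying at 50% in control and 50% falling to 25% in treated:

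| ρ | Arm-by-time, independence | Arm-by-time, covariance included | 48 hours alone |
|---|---|---|---|
| 0.2 | 0.50 | 0.59 | 0.77 |
| 0.3 | 0.50 | 0.65 | 0.77 |
| 0.5 | 0.49 | 0.79 | 0.77 |

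- The 48-hour comparison uses one record per child and has no correlation problem: its type I error under no effect is 0.041-0.050.

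**The case against.** The strongest reply is that the pairing problem has no data to act on. With no baseline scheduled for any listed categorical outcome, there are no two correlated records at the stated times. An analyst could simply compare arms at 48 hours, which is sound. This reply stands in part: for these outcomes the first defect is the missing baseline, not a mis-stated correlation. But comparing arms at 48 hours alone is not the stated rule, and the stated rule cannot be carried out on the outcomes it is written for.

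Second, the plan never says that records are treated as independent. It uses the term generalized linear model loosely, even for the mixed model, and separate models at each time are another possible reading. This also stands: independence is inferred from silence. The contrast of times does point to one joint model, and the sentence on consistency names no child effect.

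Two stronger readings are tempting and are not supported.

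- **Inflated false positives.** Under independence, an arm effect averaged over both times would reject too often: 0.084-0.085 at ρ = 0.3 and 0.105-0.109 at ρ = 0.5. The plan names no such averaged effect. The contrast it does name errs the other way.
- **The same error across all the 6-hourly readings, by substituting an early post-operative value for baseline.** Nothing in the documents proposes that substitution. Nausea is listed among the other variables, not the outcomes. Inotropic group is defined by the highest level over the two periods, although Appendix B prints a 6-hourly schedule beside it.

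**Conclusion.** The point holds in this form: the categorical rule fails as written for the outcomes listed, and it is incomplete for any outcome that does have two records per child.

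- **Without baseline variation**, the arm-by-time contrast cannot be estimated and hides a 48-hour difference (p = 1.00 against 0.032 in the illustration). This follows from the schedule and the outcome definitions. It assumes that children enter as event-free.
- **With two real records**, an ordinary model gives a conservative test that loses power: 0.50 against 0.65 at ρ = 0.3, and 0.49 against 0.79 at ρ = 0.5, in one assumed scenario. If ρ is near zero the loss disappears.

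A reader might infer that the trial's p-values in general are wrong. They are not. Troponin I is continuous, and the within-child difference handles its pairing. The sample size ("The total estimated sample size is 108 patients, over the two years, with 54 allocated to each group") does not rest on this analysis. The point is confined to categorical outcomes and should be corrected before the data are analysed.

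**What to change.** Replace the two-time contrast for categorical outcomes with one record per child. Regress status at 48 hours, or worst category up to 48 hours, on arm by logistic or ordinal regression. State in advance which of the two is used for each outcome. Include a baseline covariate only where one is actually measured.

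Where repeated records are kept, use the mixed-effects logistic model or GEE already named in the plan. Name the arm-by-time contrast as the test, and start from the first time at which the outcome can vary. Neither method rescues a baseline that is the same for every child.

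The cost is SAP wording only: no new data, no change to the sample size, and the same software.
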